2.4. Booster Neutralizing Antibodies against COVID-19

Convalescent plasma is collected from people who have completely recovered from COVID-19. Because the limited number of patients who can provide convalescent plasma, there is a limit on supply. In addition to neutralizing antibodies, there are anti-N protein antibodies and other antibodies in convalescent plasma. So the concentration of neutralizing antibodies may be low due to the presence of non-neutralizing antibodies and the therapeutic effect could be limited and inconsistent. Therefore, it is urgent to develop a safe and effective neutralizing antibody for the treatment of COVID-19.

2.5. SCTA01 is a Neutralizing Antibody against SARS-CoV-2

SCTA01 is a potential therapeutic biologic independently developed by Sinocelltech, Ltd. (SCT), a biotech company based in Beijing, China. It is a recombinant humanized anti-receptor binding domain (RBD) of the SARS-CoV-2 spike (S) protein monoclonal antibody. The antibody is an IgG1 with the Fab region having high specificity and affinity for the RBD and S protein, blocking their binding to a human receptor (specifically ACE2), and the Fc region having specific sequence modifications to significantly reduce its ability to interact with human Fc receptors and complement, thereby significantly reducing potential side effects, such as antibody-dependent enhancement (ADE) of virus infection. Consequently, it is expected that SCTA01 would likely be better in the safety profile in comparison with other anti-RBD or S protein monoclonal antibodies without such binding reduction to Fc receptors and complement.

2.6. Preclinical Pharmacokinetics

SCTA01 is a recombinant humanized anti-SARS-CoV-2 monoclonal antibody that targets the RBD of the S protein of SARS-CoV-2. Therefore, there is no pharmacologically relevant animal species that can be used to conduct pharmacokinetic studies. As a result, the preliminary pharmacokinetic study was conducted in C57BL/6 mice, and the dynamic changes of the drug in the body were studied through tail vein injection to obtain the relevant PK parameters. Moreover, SCTA01 was administered via intravenous infusion to rhesus monkeys with a single dose at 150 and 500 mg/kg, which can obtain the PK characteristics of SCTA01 in non-human primates.

Six C57BL/6 mice were selected, half male and half female. The dose for a single administration was 5 mg/kg, and the dose volume was 10 mL/kg. The pharmacokinetic results showed that SCTA01 administered to mice at a single dose of 5 mg/kg through the tail vein had normal PK characteristics. The serum drug concentration gradually decreased, the average C_{max} and AUC_{last} were 122.81 $\mu\text{g}/\text{mL}$ and 16530.33 $\text{h}\cdot\mu\text{g}/\text{mL}$, respectively. The average $t_{1/2}$ was 260.21 h, and the CL was 0.25 mL/h/kg.

Toxicokinetics (TK) was combined with the extended single-dose toxicity study in rhesus monkey. The serum concentration of SCTA01 in rhesus monkeys was analyzed using a validated ELISA method. After the administration of 150 and 500 mg/kg of SCTA01 to rhesus monkeys, the serum drug concentration correlated positively with the dose, and no significant gender difference was observed.

The ratio of the two SCTA01 dose groups is 1:3.33, the C_{max} was 3.98 mg/mL and 12.3 mg/mL (ratio 1:3.09), respectively, and the AUC_{last} was 117 h·mg/mL and 375 h·mg/mL (ratio was 1:3.21), respectively. The systemic drug exposure was basically dose-dependent. Moreover, the pharmacokinetic parameters (0~336 h) of rhesus monkeys in the 500 mg/mL high-dose group show that the average half-life ($t_{1/2}$) was 239 ± 54.3 h, the average C_{max} and AUC_{last} were 12.8 ± 0.826 mg/mL and 1460 ± 153 h·mg/mL, respectively, indicating slow drug metabolism and high systemic drug exposure.

2.7. Preclinical Pharmacodynamics

In vitro studies conducted by SCT have shown that SCTA01 can bind to the SARS-CoV-2 RBD protein and effectively block its binding to ACE2 receptors, and has a strong neutralization effect. Neutralization tests with both the SARS-CoV-2 pseudo viruses and the natural viruses confirmed the ability of SCTA01 to effectively neutralize the viruses. The binding affinity of SCTA01 under lower pH conditions (i.e., pH 5.0, pH 6.0) was similar to that under neutral pH, indicating that the antibody-virus complex can maintain a stable state, thereby capable of reducing the binding of the virus to the ACE2 receptor. Therefore, under the acidic conditions of cells, SCTA01 can inhibit the formation of virus-induced syncytia (Figure 2). SCTA01 can also effectively bind and neutralize the world pandemic SARS-CoV-2 strain (D614G mutant strain) and all known global RBD mutant strains. Overall, these results showed that SCTA01 can bind and neutralize the SARS-CoV2 virus and be a good candidate for the effective therapeutic and passive prevention of COVID-19.

[figure not shown]

Figure 2. SCTA01 Inhibits Formation of Syncytium in Virus

Antibody-virus complexes captured by immune cells (such as pulmonary macrophages), may cause antibody-dependent enhancement (ADE) of viral infections. The constant region of the SCTA01 heavy chain has a LALA mutation, which is shown experimentally to reduce the ability to bind to both Fc receptors and C1q complement. Furthermore, SCTA01 showed clearly both the reduction in inducing ADE in the *in vitro* model transfected cell lines and superiority over other anti-RBD or S protein monoclonal antibodies without the LALA mutation. As a result, the potential of ADE caused clinically by this antibody therapy can be significantly reduced or avoided.

SCTA01 showed protective effect against SARS-CoV-2 infection in two mouse models (Figure 3), the SARS-CoV-2 challenged human ACE2 transgenic mice and the mouse-adapted SARS-CoV-2 strain challenged BALB/c mice. Experiments with SCTA01 in both prophylaxis and treatment showed that it can reduce viral loads in lung and reduce lung inflammation. The pathological results showed that SCTA01 reduced lung inflammation, and no enhanced inflammation (i.e. no ADE) was detected compared to the untreated model group.

[figure not shown]

Figure 3. Protective Effect against SARS-CoV-2 Infection in Two Mouse Models

Furthermore, in a SARS-CoV-2-challenged rhesus macaques model, SCTA01 50 mg/kg intravenously 4 h after challenge showed significant virus-clearance effect (the virus loads of lung and upper respiratory tract tissues were undetectable upon treatment with SCTA01 compared with dilution buffer control animals) in the infected monkey model (Figure 4). The pathological results showed that SCTA01 also reduced viral loads of throat swabs, nasal swabs and anal swabs of rhesus macaques after SARS-CoV-2 infection. The pathological results showed that SCTA01 reduced lung inflammation, and no clear ADE phenomenon had been observed.

[figure not shown]

Figure 4. Virus RNA Copies of Different Tissues after SARS-CoV2 Infection in Rhesus Monkey

2.8. Preclinical Toxicology

Complete toxicology investigation was conducted for SCTA01 according to the latest ICH regulatory guidance to support a single-dose application in the clinical trial. All of the toxicity studies were completed in strict compliance with the Good Laboratory Practice (GLP). Toxicology studies included the assessments of seven different aspects, such as tissue cross-reactivity, safety pharmacology, extended single-dose toxicology, local irritation, immunogenicity, immunotoxicity and *in vitro* hemolysis test.

1) Extended single-dose toxicity study

The objective of this study was to evaluate the toxicity, target organ of toxicity and toxicokinetic profile of SCTA01 after a single dose administration in rhesus monkeys via intravenous infusion with a 2-week observation period, to determine the maximum tolerated dose, and to provide reference for dose design and toxic side effects monitoring in clinical trials.

The study design was as follows: vehicle control group (5 animals/sex/group), 150 mg/kg group (3 animals/sex/group) and 500 mg/kg group (5 animals/sex/group). On Day 1, a single dose was given to monkeys by intravenous infusion. The dose volume was 20 mL/kg, and the administration rate was about 0.5 mL/kg/min.

Analyzed items included: clinical observation, weight, food consumption, body temperature, electrocardiogram, respiration, blood pressure, ophthalmoscopic examinations, hematology, coagulation, clinical chemistry, urinalysis, T lymphocyte subsets (CD3⁺, CD3⁺ CD4⁺, CD3⁺ CD8⁺ and CD3⁺ CD4⁺ / CD3⁺CD8⁺), cytokines (IL-2, IL-4, IL-5, IL-6, TNF- α , IFN- γ), serum complement determination (C3 and C4), immunoglobulin (IgA, IgM and IgG), C-reactive protein, serum anti-drug antibodies and toxicokinetics. On the third day after administration, the first 3 animals in all groups are euthanized, and the remaining 2 animals/sex/group were euthanized at the end of the observation period of 2 weeks after administration. Complete autopsy was conducted on all animals. In addition, organ weight, gross and microscopic observation were also performed.

Throughout the study, no mortality was recorded in any group. No changes related to the test articles were noted in clinical observation, body weight, food consumption, electrocardiogram, blood pressure, respiratory function, ophthalmoscopic examinations, hematology, clinical chemistry, urinalysis, T lymphocyte subsets, cytokines, complement, immunoglobulin and C-reactive protein, organ weight, gross and microscopic observation in any group throughout the study.

The serum concentration of SCTA01 in rhesus monkeys was analyzed using a validated ELISA method. After the administration of 150 and 500 mg/kg of SCTA01, the serum drug concentration was positively correlated with the dose, and no significant gender difference was observed.

In summary, this study showed that when SCTA01 was administered to rhesus monkeys by intravenous injection in single doses of 150 and 500 mg/kg, no obvious toxicity was observed, and the maximum tolerated dose (MTD) was considered to be 500 mg/kg, which could also be thought as No Observed Adverse Effect Level (NOAEL) due to the single injection in clinical use.

2) Immunogenicity

Immunogenicity testing was conducted in the extended single-dose toxicity study in rhesus monkeys by testing for the presence of anti-drug antibodies and their potential impact on efficacy and toxicity. No anti-drug antibody was detected in any group at all of the time points, and there is no immunogenicity in rhesus monkey with this single-dose administration of SCTA01. The results showed that SCTA01, when given to rhesus monkeys by intravenous infusion at a single dose of 150 and 500 mg/kg, did not induce ADA.

3) Immunotoxicity

The immunotoxicity of SCTA01 was assessed in the extended single-dose toxicity study in rhesus monkeys.

The results showed that there was no significant effect of SCTA01 on the counts of white blood cells (WBC), WBC subtypes, T lymphocyte subsets, immunoglobulin (IgA and IgM), complement (C3 and C4), C-reactive protein, gross and microscopic observations of immune organs (thymus, spleen, lymph nodes), organ weight or ratios.

On Day 3, in the test group at a dose of 500 mg/kg, both male and female monkeys had a statistically significant increase in IgG. Considering that the test article was an IgG monoclonal antibody and the amount injected relative to the total monkey blood volume, the observed elevated IgG was considered to have no toxicological significance.

In short, there was no immunotoxicity observed with the test article.

4) Local tolerance

Local tolerance study was conducted with the extended single-dose toxicity study in rhesus monkeys to evaluate the effect of SCTA01 on local irritation at the infusion site. During the experiment, local reactions were assessed on dosing day (prior to dosing) and Day 2, for visible and palpable changes. After the end of the administration and recovery period, the animals were euthanized, the macroscopic and microscopic observations of the injection site were conducted.

The results showed that no abnormal changes were found in the injection site of any group, and no changes related to the test article were observed in the gross and microscopic observations during the entire study.

In summary, SCTA01 given to rhesus monkeys by intravenous infusion, with a single dose of 150 and 500 mg/kg, indicated that no irritation of the injection sites occurred.

5) Safety pharmacology

This study was combined with an extended single-dose toxicity study in rhesus monkeys to reveal any functional effects on the major physiological systems (e.g., cardiovascular, respiratory, and central nervous systems). The results showed that there were no abnormal changes in the mental state and behavior of all monkeys. There were no changes in the heart rate, ECG wave, PR interval, QRS time limit, QT interval and QTc values at any time point in any group. During the entire study, no abnormal changes in the blood pressure (mean arterial pressure, diastolic blood pressure, and systolic blood pressure) were observed. The tidal volume (TV, mL) of female monkeys administered at a dose of 500 mg/kg of SCTA01 showed a statistically significant decrease prior to dosing and approximately 2 to 4 hours after administration on the first day. These changes were not considered to be related to the test article, because the observed tidal volume value occurred prior or close to the dosing.

In summary, during the entire study, no changes in the clinical parameters in any group related to the test samples were observed. Compared with the vehicle control group, no biologically significant changes in body temperature, blood pressure, pulse rate or ECG parameters were found in animals administered with 150 and 500 mg/kg of SCTA01. After intravenous injection of SCTA01 of a single dose of 150 and 500 mg/kg in rhesus monkeys, there was no significant effect on the rhesus monkey's nervous system, cardiovascular system and respiratory system.

6) Tissue cross reactivity studies of normal human and rhesus monkey

Streptavidin-biotin immunohistochemical method was used to evaluate the tissue cross reactivity of SCTA01 monoclonal antibody in frozen normal human and rhesus monkey tissues. Each tissue came from three different donors. The test consisted of two test item groups with different concentrations (SCTA01 injection/biotin, 1.0 µg/mL and 10.0 µg/mL), an isotype control group (human IgG1, κ isotype control biotin, 10.0 µg/mL) and a negative control group (phosphate buffered saline containing Tween 20).

As a result, a brown positive staining signal was observed in the cell membrane/cytoplasm of the positive control slide in all test groups. No positive staining was observed in the slides of 34 types of frozen normal human tissues or frozen normal rhesus monkey tissues.

In conclusion, under the conditions of this study, SCTA01 did not specifically bind to frozen normal human and rhesus monkey tissues.

7) *In vitro* hemolysis test

This *in vitro* study evaluated the hemolysis or aggregation effect of SCTA01 using human red blood cells. A positive control group (sterile water for injection), a negative control group (sodium chloride injection) and 5 tubes of SCTA01 (0.5, 0.4, 0.3, 0.2, 0.1 mL/tubes, 25 mg/mL SCTA01) were used. The results showed that complete hemolysis occurred in the positive control tube, but no hemolysis or aggregation was observed in the test product and the negative control tube.

Therefore, under the conditions of this study, 25 mg/mL of SCTA01 had no hemolytic or aggregation effect on human RBCs.

2.9. Clinical Experience and Dose Selection

A Phase Ia study: the first-in-human study (SCTA01-X101, NCT number: NCT04483375) is being conducted in China in healthy subjects to assess the safety and tolerability of SCTA01, as well as to determine its PK and immunogenicity profile.

The available data as of 21 Sep 2020 of the Phase Ia study showed no observed dose limiting toxicities (DLT) after the completion of all four dose groups (each dose group consisted of placebo and either 5 or 15 or 30 or 50 mg/kg) in 33 healthy volunteers. The human experience of SCTA01 indicated that SCTA01 is safe and well-tolerated at all four tested dosing levels. There have been no serious adverse events (SAEs) or deaths reported, and all of adverse events have been transient and mild or moderate in intensity observed while treatment assignment has remained blinded.

The available preliminary PK data for the four doses (5, 15, 30 and 50 mg/kg) showed normal dose-dependent clearance, as expected for an IgG single-dose PK in human when the IgG has no *in vivo* target. The concentration-time curve of each group is shown in Figure 5. The PK parameters of each group is shown in the Table 1.

[figure not shown]

Figure 5. Mean Concentration-time Curves of SCTA01 at 5, 15, 30 and 50 mg/kg Level from Interim Data of Phase Ia Trial in China

Table 1. Pharmacokinetic Parameters of SCTA01 from Non-compartmental Analysis

	T _{1/2} (h)	T _{max} (h)	C _{max} (ng/mL)	C _{last} (ng/mL)	AUC _{0-Day28} (h*ng/mL)	AUC _{0-t} (h*ng/mL)	AUC _{0-∞} (h*ng/mL)	Vd (L)	C (L/h)
5 mg/kg (n=3)	1040 (15.7%)	1.32 (0.32 ~ 1.32)	84800 (7.7%)	19900 (14.6%)	26900000 (8.5%)	34500000 (9.6%)	64400000 (14.6%)	7.06 (9.8%)	0.00475 (12.4%)
15 mg/kg (n=6)	821 (29.2%)	1.92 (0.92 ~ 8.92)	307000 (15.6)	70300 (11.7%)	89900000 (9.3%)	118000000 (9.0%)	201000000 (14.8%)	5.92 (19.6%)	0.00516 (14.8%)
30 mg/kg (n=8)	574 (25.1%)	2.83 (1.83 ~ 9.83)	607000 (13.8)	176000 (9.8%)	185000000 (9.5%)	185000000 (9.5%)	331000000 (14.5%)	4.57 (23.2%)	0.00558 (11.9%)
50 mg/kg (n=8)	625 (19.9%)	3.16 (3.15 ~ 3.17)	1040000 (6.1%)	270000 (9.1%)	286000000 (8.2%)	287000000 (8.2%)	532000000 (12.8%)	5.12 (13.2%)	0.00581 (18.5%)

Data are presented as the arithmetic mean (coefficient of variation), T_{max} data is median (range).

T_{1/2} = half-life. T_{max} = time of maximum concentration. C_{max} = maximum concentration. C_{last} = concentration at last sample time point. AUC_{0-t} = area under the concentration-time curve from time of dose to last sample time point. AUC_{0-Day28} = area under the concentration-time curve from time of dose to Day 28 time point. AUC_{0-∞} = area under the concentration time curve from 0 hour to infinity.

The data is from the interim report of SCTA01-X101. The cutoff time is 21th Sept, 2020. The last time point of 5 mg/kg and 15 mg/kg groups were Day 42, 30 mg/kg and 50 mg/kg groups were Day 28.

Detailed safety and PK data of all groups are available in the Investigator Brochure (IB).

Since there is no specific binding target in animals and healthy subjects who have not been infected by SARS-CoV-2, the No Observed Adverse Effect Level (NOAEL) in monkey is 500 mg/kg. If calculated by the area normalization method of body surface¹⁹, the human equivalent dose is 200 mg/kg. When the safety factor is set to equal 10, the initial dose will be 20 mg/kg. Based on the results of the *in vivo* pharmacodynamic study and the fact that there is no toxicity observed, as well as the initial doses of other similar antibody products for Phase I that have been reported, SCT started the initial human dose at 5 mg/kg, and increased in the escalating steps to 15 mg/kg, 30 mg/kg and 50 mg/kg in Phase Ia study in China. SCTA01 20 mg/kg can significantly reduce the viral load of lung and bronchus in humanized ACE2 mouse model for SARS-CoV-2 infection. The pathological results of mouse model showed that the infected tissue was mainly limited at the lungs with mild lung interstitial lesions, the same as those in mild/moderate infection in COVID-19 patients²⁰. However, SARS-CoV-2 can be detected in multiple organs in severe patients, including the lungs, pharynx, heart, liver, brain, and kidneys, which indicate its broad organ tropism^{21, 22}. The mean viral load of severe cases was around 10~60 times higher than that of mild cases, suggesting that higher viral loads might be associated with severe clinical outcomes and high risk of death²³⁻²⁶. Therefore, clinical dosage should be increased compared with the mouse model. SCTA01 50 mg/kg has shown significant antiviral effect in the pre-clinical study of monkey model of SARS-CoV-2 infection with excellent safety profile. So the 50 mg/kg will be chosen as the higher dose of this study.

Recently, the data published by Lilly and Regeneron showed that the efficacy may not be dose dependent^{27,28}, which indicated that lower dose maybe also have similar efficacy with better safety profile compared to higher dose. Therefore, SCT selects 15 mg/kg as the lower dose, which corresponds to approximately 20 mg/kg.

Based on the preclinical study data, the safety and PK data of Phase Ia and the high viral loads observed in severe COVID-19 subjects, SCT proposes SCTA01 15 mg/kg and 50 mg/kg as doses of Phase II part, and the dose of Phase III part will be determined by Phase II part results.

2.10.Rationale

The preclinical and clinical data of SCTA01 merit a Phase II part with the SCTA01 15 mg/kg, SCTA01 50 mg/kg and placebo to evaluate the safety and efficacy of SCTA01 in severe patients with COVID-19 and a Phase III part with the single dose of SCTA01 (X mg/kg or X mg) selected through Phase II results to evaluate the safety and efficacy of SCTA01 in patients with severe COVID-19.

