7.4.1. Viral Load Assessment in NP or OP Swab Samples

As outlined on the Tables 3 and 4, NP or OP swab samples will be collected on Day 1; and Days 3, 5, 8, and 11 (while hospitalized); and on Days 15, 29, 120 (if attends an in-person visit or still hospitalized) or at early withdraw. Up to 29 days after administration, subjects who are virus positive should continue to undergo regular viral testing by NP or OP swab samples until the viral RNA test is negative.

NP samples should be taken from the same nostril for all tests.

If NP swab samples are not obtainable, oropharyngeal (OP) swab samples may be substituted, but make sure the position of swabs are consistent for the same subject.

Quantitative PCR for NP or OP swab samples will be done at central lab.

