9.3. Statistical Decision Rules

A combined *p*-value using inverse normal method of less than 1-side of 0.01068 from 3rd interim analysis or less than 1-side of 0.0166 from final analysis will need to be observed to declare statistical significance. The total number of patients in the ITT analysis sets for primary analysis will include patients in the recommended dose group in Phase II and in the same dose group that continued in Phase III, or the control group. i.e., 95 + 255 = 350 patients for recommended dose group or for control group. The patients from the inferior dose group (95 patients) in Phase II will only contribute to the multiplicity penalty of dose selection.

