9.4. Sample Size

The treatment estimates are based on the study ACTT-1 of Remdesivir[®] for COVID-19. Under the TTCI definition used in this study, rate ratio (RR) for recovery for the severe patients, the patients with 5-point of baseline ordinal score and the patients with 6-point of baseline ordinal score is 1.31, 1.45 and 1.09 respectively^{31,32}. The event rate for the patients with 5-points is 88.8% and 76.8% for Remdesivir[®] group and placebo group, respectively. The assumption to calculate the sample size is set on the results from 5-points patients, which is RR as 1.4 and event rate as 80%. The sample size determination assumptions aim at a more meaningful clinical difference under a stricter TTCI definition.

Sample size is calculated based on the following assumptions:

- Overall Type-I error rate should not exceed 2.5% (1-sided);
- Rate ratio (RR) sets to be 1.4 (if the median TTCI is 9 days on the placebo group, the SCTA01 group will be 6.5 days under the assumption of Exponential distribution);
- Randomization ratio of study drug group and placebo group in Phase III is 1:1;
- Randomization ratio of medium dose group, high dose group and placebo group in Phase II is 1:1:1;
- 80% event rate;
- Sample size ratio of Phase II and Phase III is 1:1.79;
- Simes method will be applied to attain adjusted *p*-value from Phase II;

- Inverse normal weighting method will be used to combine *p*-value from Phase II and Phase III part;
- The 3rd interim analysis, which is the penultimate analysis for superior efficacy stopping and futility analysis, will be conducted when 31% of the TTCI events have been observed from the Phase III part;
- Pocock boundary (Lan DeMets 1983) will be used to control overall Type I error within 1-sided 2.5%;
- The critical values of nominal *p*-value will be re-calculated based on the actual number of TTCI events documented at the time of interim analysis and final analysis.

The study will randomize 795 patients totally, with Phase II of 285 patients and Phase III of 510 patients (255 in each group), providing over 90% power.

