9.7. Efficacy Analysis

9.7.1. Primary Efficacy Analysis

The primary endpoint is TTCI up to Day 29. TTCI is defined as the time (in days) from randomization to the first day on which a patient satisfies point 1, 2, or 3 on the 8-point ordinal scale and maintains a score ≤ 3 at least 48 hours (initial improvement) and maintains this up to Day 29 (sustained improvement).

All deaths within 29 days or terminated early due to AE will be designated censored at Day 29 with respect to primary endpoint. Any subjects lost to follow-up or terminated early due to other reasons prior to an observed primary endpoint will be censored at the day of their last observed assessment. Subjects who completed follow-up but did not experience a primary endpoint event will be censored at the day of their Day 29 visit. The subjects who take prohibited medications will be regarded as treatment failures and will be censored at the time of medication use.

The primary analysis will use the stratified log rank test to compare treatment group to control group through Day 29 with respect to primary endpoint. Covariate factors may include country, duration of symptoms prior to enrollment, comorbidity and best supportive treatment. Note that if some strata are too small, they might be combined together to allow statistical method work well.

For each group, the Kaplan-Meier estimate of TTCI survival function will be constructed. Hazard ratio of SCTA01 vs. placebo with two-sided 95% CI will be derived from the stratified Cox proportional hazard model. The number of patients with a TTCI event and number of patients censored for the TTCI analysis will be summarized by treatment group.

The sensitivity analyses (such as using different population, different censoring rules and/or different covariates) for the primary endpoint will be fully described in the statistical analysis plan (SAP).

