9.7.7. Sub-group Analyses

Subgroup analyses for the primary outcomes will evaluate the treatment effect across the following subgroups: country, race, ethnic group, duration of symptoms prior to enrollment, age, sex and comorbidity, best supportive treatment. A forest plot will display confidence intervals across subgroups. Interaction tests will be conducted to determine whether the effect of treatment varies by subgroups.

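### Baseline viral load, sampled before infusion in all patients, is not named as a factor in the primary TTCI analysis or as a subgroup; if it is prognostic among score-5 patients, leaving it out gives away some power

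*Combined protocol and SAP*

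**What the plan says.** Section 2.9 reports that mean viral load in severe cases was about 10 to 60 times that in mild cases, "suggesting that higher viral loads might be associated with severe clinical outcomes and high risk of death", and uses this to argue for a clinical dose above the one used in mice.

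Section 7.4.1 states that "NP or OP swab samples will be collected on Day 1". Table 3 places that sample before infusion, with an oropharyngeal (OP) swab as substitute if a nasopharyngeal (NP) swab cannot be taken. The PCR is quantitative and done centrally.

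Section 9.7.1 plans a stratified log-rank test, with the hazard ratio from a stratified Cox model. On the factors it says: "Covariate factors may include country, duration of symptoms prior to enrollment, comorbidity and best supportive treatment". Other covariates appear only as a possible sensitivity analysis, deferred to the SAP with none named. Section 9.7.7 lists the subgroups as "country, race, ethnic group, duration of symptoms prior to enrollment, age, sex and comorbidity, best supportive treatment", with interaction tests. Baseline viral load is in neither list. Randomization (5.6) is stratified by country only. Section 1.3 gives baseline antibody level an exploratory objective; baseline viral load has none.

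The planning assumption in 9.4 is the one "which is RR as 1.4 and event rate as 80" per cent, with over 90% power. Under 9.3 the combined p-value must be "less than 1-side of 0.01068 from 3rd interim analysis" or "less than 1-side of 0.0166 from final analysis".

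**The concern.** A log-rank or Cox analysis that leaves out a prognostic baseline variable estimates a hazard ratio closer to 1 than the one conditional on that variable, and it has less power. Baseline viral load is a natural candidate here. The protocol itself raises a link with outcome, the value is collected before treatment, and the product is an antiviral antibody whose Phase III dose is chosen on Day 8 viral load.

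Three things are at stake. The first is final power. The second is the observed rate ratio (RR) that is set against the futility bounds of 1.15 (end of Phase II) and 1.22 (third interim). The third is whether the trial will report if the effect varies with baseline viral load, which no planned analysis examines.

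**Working it through.** **Step 1: reproduce the plan's figures.** Inputs: RR 1.4, 80% events, 95 + 255 = 350 patients per arm, 556 final events, final one-sided level 0.0166 (z = 2.130).

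- Interim level: Lan-DeMets Pocock spending at 31% information is 0.025 × ln(1 + (e − 1) × 0.31) = 0.01068, as stated. The matching final level is 0.0167 (0.0166 at 31.4% information).
- Power by Schoenfeld's formula: ln(1.4) × √556 / 2 = 3.967, and Φ(3.967 − 2.130) = 96.7%.
- Simulating the planned test (Simes, inverse normal, both boundaries, both doses at RR 1.4, futility not enforced) gives 96.4 to 96.6%.
- For 90% power, 412 events would do. The claim of over 90% therefore reproduces with a margin.

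**Step 2: effect of leaving viral load out.** The documents give no prognostic strength, so a range is assumed for the hazard ratio per SD of log viral load (higher load, slower improvement). Simulation: 1,500 trials per setting, 700 patients, exponential times, 80% events by 28 days, normally distributed log viral load, conditional RR 1.4, Cox model without and with viral load, one test at 0.0166. The last column is (mean Z adjusted / mean Z unadjusted)².

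| Hazard ratio per SD | RR without / with | Power without / with | Efficiency ratio |
|---|---|---|---|
| 1.0 | 1.40 / 1.40 | 97% / 97% | 1.00 |
| 1.2 | 1.39 / 1.40 | 96.6% / 97.3% | (3.964/3.894)² = 1.04 |
| 1.35 | 1.38 / 1.40 | 95.3% / 96.6% | (3.947/3.759)² = 1.10 |
| 1.5 | 1.36 / 1.40 | 92.7% / 96.9% | (3.975/3.632)² = 1.20 |
| 2.0 | 1.31 / 1.41 | 86.1% / 97.2% | (4.011/3.189)² = 1.58 |

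Unadjusted power crosses 90% somewhere between 1.5 and 2.0 per SD. With no treatment effect, the unadjusted test rejected in 0.020 and 0.016 of trials at 1.5 and 2.0 per SD (simulation SE 0.003, nominal 0.0166), so type I error is not disturbed.

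**Step 3: effect on the futility comparisons.** Table 7 gives 149 and 280 events, so the SE of log RR is about 2/√149 = 0.164 and 2/√280 = 0.120. The chance that an effective dose falls below a bound is Φ[(ln bound − ln RR)/SE].

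| Expected RR | Below 1.15 at 149 events | Below 1.22 at 280 events |
|---|---|---|
| 1.40 | Φ(−1.20) = 11% | Φ(−1.15) = 12% |
| 1.38 | Φ(−1.11) = 13% | Φ(−1.03) = 15% |
| 1.36 | Φ(−1.02) = 15% | Φ(−0.91) = 18% |
| 1.31 | Φ(−0.80) = 21% | Φ(−0.60) = 28% |

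**Step 4: sensitivity.** If 12% of patients never improve, independently of viral load, adjustment gains about 0, 5 and 7 points at 1.2, 1.5 and 2.0 per SD. Missing swabs, or a mix of NP and OP specimens, would shrink the gains further; the simulation assumed a complete and error-free covariate.

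**The case against.** The strongest reply is that the premise is thin. Section 2.9 is hedged and contrasts severe with mild cases, whereas the trial enrols score 5 only. The outcomes it mentions are severity and death, while the endpoint is time to sustained improvement. It does not say which specimen was measured. A between-severity contrast gives no prognostic strength within one severity class. This stands, and it is why every loss above is conditional.

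Second, fixing the conditional RR at 1.4 builds the loss in. The documents take 1.4 from an external remdesivir trial and do not say whether it was adjusted for viral load. If it was not, the stated power already reflects the omission and adjustment is a gain over plan. The attenuation is then a change of estimand and not a bias. This also stands. Stratifying on symptom duration or comorbidity, if correlated with viral load, would recover part of the gain.

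Third, the factor list is open and the SAP may add covariates. That means adjustment is not ruled out; it does not mean it is planned. A covariate first named after unblinded efficacy results would be hard to defend.

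Fourth, the 1.15 bound is non-binding, and 9.7.5 says only that the 1.22 bound may be used, although the synopsis and 3.1 word it as a firm rule. Chance imbalance in viral load between Phase II arms is part of ordinary sampling error (SE about 0.16 on the log scale) and needs no separate argument.

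A reader might also infer that section 2.9 presumes the antibody works mainly in patients with high viral load. It does not: it uses viral load only to support a higher dose than in mice. Absence from the subgroup list costs no power; it only leaves that question unexamined.

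**Conclusion.** The omission from both lists is real, and naming the variable would be a cheap gain in efficiency. At a conditional RR of 1.4 the power lost is nothing if viral load is not prognostic, about 1 point at 1.2 to 1.35 per SD, about 4 points at 1.5 and about 11 points at 2.0. The observed RR falls to 1.39, 1.38, 1.36 and 1.31 at 1.2, 1.35, 1.5 and 2.0 per SD. Adjusting costs no power if viral load turns out not to matter.

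These sizes rest on an assumed prognostic strength, proportional hazards, complete swabs and a single final test without futility stopping. It would be tempting to conclude that the trial is underpowered or its primary result biased. The documents do not support that: type I error holds, and the stated power of over 90% survives up to about 1.5 per SD. Nor do they establish that viral load is prognostic in this population. The point is an improvement to make, not an error in the plan.

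**What to change.** Before any unblinded efficacy analysis (the first interim already allows a preliminary efficacy look):

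- In 9.7.1, name log10 Day 1 pre-infusion viral load as a covariate in the stratified Cox model for TTCI. Set undetectable values to the assay limit, state a missing-value rule, and record specimen type (NP or OP).
- If the stratified log-rank test stays the primary test, add a two-level viral-load stratum cut at the blinded pooled median. Let it replace a weaker optional factor, since 9.7.1 already foresees strata that are too small. A median split recovers part of the gain: about 12% in efficiency, against 19 to 20% for the continuous covariate, at a log-hazard SD of 0.4 (about 1.5 per SD).
- Add baseline viral load to the subgroup and interaction tests in 9.7.7.
- If the sponsor prefers to leave it out, say why.

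The cost is wording only, with no new samples. The Day 1 laboratory data must be clean at each analysis, and the hazard ratio becomes conditional on viral load. Taking the p-value from the Cox model would replace the planned log-rank test, so the choice between the two must be explicit. Missing or mixed specimens reduce the gain.
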